1. VERSION HISTORY

Table 1. Summary of Changes

Version/ Date	Associated Protocol Amendment	Rationale	Specific Changes
V1	Amendment 4	Original SAP	No

2. INTRODUCTION

Gaucher disease (GD) is a rare genetic disorder of lipid metabolism and is the most common inherited lysosomal storage disorder, thought to affect around 10,000 people globally. Gaucher disease is classified into 3 major phenotypic subcategories based on the absence (Type 1) or presence and severity (Types 2 and 3) of primary central nervous system involvement. Gaucher disease Type 3 (except Type 3c), the population under study in this current protocol, affects approximately 5% of documented GD cases. Type 3 GD is associated with progressive neurodegenerative disease, with symptom onset usually between infancy and adolescence. Manifestations of Type 3 GD vary among patients, ranging from visceral and bone disease, cytopenia, hearing impairment, supranuclear gaze palsy, developmental delay, and cardiac calcification to myoclonic encephalopathy with seizures and eventual death.

Taliglucerase alfa, a hydrolytic lysosomal glucocerebroside-specific enzyme for intravenous infusion, is a recombinant active form of the lysosomal enzyme, β -GCD (β -glucocerebrosidase), produced using transgenic carrot plant root cells grown in suspension culture with a modified gene sequence encoding human β -GCD. Taliglucerase alfa is currently an approved therapy in the United States and many other countries for adults and children with a confirmed diagnosis of Type 1 GD, and is also approved for use in Type 3 GD in a small number of countries.

The effects of enzyme replacement therapy (ERT) on patients with Type 1 GD have been clearly documented and have a beneficial effect on visceral and hematologic disease parameters. It is known that recombinant enzyme does not pass the blood-brain barrier and has no effect on neurologic involvement. This prospective study aims to objectively evaluate the hematologic and visceral effects of ERT with taliglucerase alfa on a rather clinically and genetically homogenous group of treatment-naïve patients with Type 3 GD. The results of this study are expected to provide a more objective view of the degree of response of this patient type, and potentially create new areas of research.

This statistical analysis plan (SAP) provides the detailed methodology for summary and statistical analyses of the data collected in Study WI224302. This document may modify the plans outlined in the protocol; however, any major modifications of the primary endpoint definition or its analysis will also be reflected in a protocol amendment.

2.1. Study Objectives, Endpoints, and Estimands

The efficacy objectives of this study are to assess the efficacy of taliglucerase alfa in subjects with Type 3 GD, as measured by percent change from baseline in spleen and liver volume evaluated by magnetic resonance imaging (MRI), hemoglobin, platelet count, and lyso-glucosylsphingosine (Lyso-Gb1); change from baseline in growth and development (height, weight, sexual development by Tanner classification, and bone age by X-ray of left hand and wrist), bone mineral density evaluated by dual-emission X-ray absorptiometry (DEXA), and evaluation of fatigue.

The safety of taliglucerase alfa will be assessed by adverse events, clinical laboratory tests, vital signs, and physical examinations. Anti-taliglucerase alfa antibodies will also be assessed.

2.1.1. Primary Estimand(s)

The primary estimand of this study uses the treatment policy strategy and estimates the effect for all participants are treated and regardless of whether an intercurrent event occurs. It includes the following 4 attributes:

- Population: All patients who suffer from the Type 3 GD as defined by the inclusion and exclusion criteria, and who have received at least one complete dose (or partial dose if adverse events prevent completing infusion dose);
- Variable: Percent change from baseline to Month 12 in spleen volume expressed in MN (Multiples of Normal) and measured by MRI (Magnetic Resonance Imaging);
- Intercurrent event: All data after an intercurrent event (discontinuation of treatment, discontinuation of study, etc), if collected, will be included;
- Population-level summary: median percent change from baseline to Month 12 and p-value from the Wilcoxon signed ranks test.

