6.3.3 Removal of Subjects from Study

Reasons for permanent discontinuation include the following:

1. The subject experiences two or more Grade 3 toxicities or one or more Grade 4 toxicity considered by the Investigator associated with taliglucerase alfa treatment (see [Section 8.2.1: Adverse Events](#); and [Appendix 14.5: WHO Common Toxicity Criteria](#))
2. The subject experiences progressive hypersensitivity or severe hypersensitivity will be treated appropriately and may be withdrawn from the study, at the discretion of the treating Investigator and/or Medical Monitor (see [Appendix 14.2: Infusion Rate Algorithm](#); and [Appendix 14.3: Taliglucerase Alfa Hypersensitivity Evaluation and Treatment Algorithm](#))
3. The subject, or subject's parent or guardian, requests to discontinue treatment
4. Investigator feels that it is not in the best interest of the subject to continue treatment and/or the Investigator believes that the subject can no longer be compliant with the requirements of the study
5. Deteriorating clinical condition, which the Investigator decides additional treatments would be needed

For any discontinuation, the Investigator will obtain all required details and document the date and the main reason for the premature discontinuation. If the reason for discontinuation is an adverse event, the specific event or the main laboratory abnormality will be recorded in the case report form (CRF). The Investigator will make thorough efforts to document the outcome. The Investigator will attempt to continue to follow the subject for the full duration of the study or at least for 30 days following discontinuation. If circumstances prevent the subject from completing all visits, every attempt will be made to complete all procedures listed in [Section 9.2.11](#) for Visit 27.

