7.9 Prior and Concomitant Therapy

Medications having the potential to interfere with the evaluation of efficacy are excluded throughout the trial.

The following medications are strictly prohibited during the study:

- Zavesca® (miglustat)
- Ceredase® (algucerase)
- Cerezyme® (imiglucerase)
- Vpriv® (velaglucerase alfa)
- Cerdelga® (eliglustat)

The following medications are allowed and expected during the study:

- Treatments for hypersensitivity, anaphylaxis, or anaphylactoid reactions, e.g., epinephrine, norepinephrine, glucagon, albuterol
- Treatments for anemia, e.g., iron, folic acid, vitamin B₁₂
- Treatments for bone disease, e.g., bisphosphonates
- Analgesics, e.g., nonsteroidal anti-inflammatory drugs (note: aspirin may be contraindicated due to its effects on platelets and risk for bleeding)

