4. ANALYSIS SETS (POPULATIONS FOR ANALYSIS)

Data for all participants will be assessed to determine if participants meet the criteria for inclusion in each analysis population prior to releasing the database and classifications will be documented per standard operating procedures.

The analysis populations for reporting are defined in the following table.

Population	Description
Enrolled	All participants who sign the informed consent document.
Evaluable or Full Analysis Set (FAS)	All enrolled participants to the study who take at least 1 complete dose of taliglucerase alfa (or partial dose if adverse events prevent completing infusion dose). Participants will be collected according to the study drug actually received for this non-randomized study.
Safety	All participants who receive at least 1 dose of study drug. Participants will be analyzed according to the study drug they actually received. An enrolled but not treated participant will be excluded from the safety analyses.
Per Protocol set (PP)	All participants who complete the primary efficacy data collection at Month 12 and baseline assessment, and receive at least 1 complete dose of taliglucerase alfa (or partial dose if adverse events prevent completing infusion dose).

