5.3. Methods to Manage Missing Data

The missing data for the primary and secondary efficacy endpoints analyzed by the Wilcoxon signed rank test will be imputed using last observation carried forward (LOCF) method in FAS, ie, the measurement obtained at the early termination visit will be used to impute the Month 12 data.

For imaging-based endpoints, the spleen volume and liver volume measured by the MRI at the early termination visit will be taken as the Month 12 measurement, if the Month 12 visit is missing. If there is no post-baseline MRI measurement, the percentage change from baseline to Month 12 in organ volumes by ultrasound can be used to impute the missing percentage change from baseline in organ volumes by MRI per clinical judgment. The percentage change from baseline needs to be derived within the same imaging test, ie, based on post-baseline organ volume measured by ultrasound and baseline organ volume measured by ultrasound. If there is no post-baseline imaging measurement, the baseline observation carried forward (BOCF) will be applied for missing data, ie, the baseline volume measured by MRI will be used to impute Month 12 MRI data.

Missing safety data will be handled according to the Pfizer Clinical Data Interchange Standards Consortium (CDISC) safety rulebook and data standard rules for imputation, including missing dates (when the date is required for a calculation) and missing severity of adverse events.

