6. ANALYSES AND SUMMARIES

6.1. Primary Endpoint

6.1.1. Main Analysis

- Estimand strategy: Treatment policy strategy for percent change from baseline to Month 12 in spleen volume MN measured by MRI.
- Analysis set: FAS (defined in [Section 4](#)). All participants assigned to study drug and received at least 1 complete dose of taliglucerase alfa (or partial dose if adverse events prevent completing infusion dose) will be included.
- Analysis methodology: Percent change from baseline to Month 12 will be analyzed using Wilcoxon signed rank test detailed in [Section 5.2.2](#). In order to judge whether this primary efficacy endpoint meets the 20% reduction from baseline, a 20% shift will be added on the percent change from baseline for each participant in the analysis set before the procedure of Proc Univariate ([Appendix 4](#)).

- Intercurrent events and missing data: Data after study drug discontinuation will be included. Missing values will be imputed using LOCF and other methods specified in [Section 5.3](#) and be included in calculating percent change from baseline.
- Summary of statistical comparison: The 2-sided p-value from the exact inference for Wilcoxon signed rank statistics for comparing Month 12 to baseline value, as well as the median percent change from baseline, will be presented and used to judge whether efficacious criteria is met. The n, minimum and maximum for the observed percent change from baseline will be presented together as well.
- Descriptive summary including n, mean, SD, median, minimum, and maximum for absolute value, change from baseline and percent change from baseline in spleen volume and spleen volume MN measured by MRI at each visit will be presented.

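### The SAP has no rule for spleen volumes measured after a switch to another Gaucher therapy, splenectomy or marrow transplant, and the per-protocol analysis does not isolate them

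*SAP*

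**What the plan says.** - **Strategy.** SAP 2.1.1: "The primary estimand of this study uses the treatment policy strategy". Its rule is "All data after an intercurrent event (discontinuation of treatment, discontinuation of study, etc), if collected, will be included". The only events named are stopping treatment and leaving the study, followed by an open-ended et cetera. SAP 6.1.1 repeats for the main analysis: "Data after study drug discontinuation will be included". SAP 2.1.2 and 6.2.1 apply the same rule to liver volume, hemoglobin, platelets, Lyso-Gb1 and chitotriosidase.
- **Substitution.** Under SAP 5.3 the early-termination MRI "will be taken as the Month 12 measurement, if the Month 12 visit is missing". With no post-baseline MRI, ultrasound may be used per clinical judgment. With no post-baseline imaging at all, baseline is carried forward (0% change).
- **Stopping and follow-up.** Protocol 6.3.3 lists as a reason for discontinuation "Deteriorating clinical condition, which the Investigator decides additional treatments would be needed". For any discontinuation it adds: "The Investigator will attempt to continue to follow the subject for the full duration of the study or at least for 30 days following discontinuation". Protocol 9.2.12 asks for the Month 12 procedures, MRI included, at early termination.
- **Other therapies.** Protocol 7.9 says "The following medications are strictly prohibited during the study" and lists five Gaucher products. It gives no rule for data collected after one of them is taken. Splenectomy and marrow transplant appear only as an entry exclusion (Protocol 6.3.2).
- **Sensitivity set.** SAP 4 defines the per-protocol set as "All participants who complete the primary efficacy data collection at Month 12 and baseline assessment, and receive at least 1 complete dose", or a partial dose if an adverse event interrupted the infusion. SAP 6.1.2 uses this set to gauge the effect of early discontinuation. SAP Appendix 2.3, on deviations that affect populations, is marked not applicable.

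**The concern.** The trial has one arm, and SAP 5.1 declares the drug efficacious if the median percent change is significantly below -20%. In a randomized trial, a treatment-policy estimand compares two policies that may each include rescue. Here the comparison is with a fixed number, so any spleen reduction produced by another Gaucher therapy is credited to taliglucerase.

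The handling is also asymmetric. A subject who fails, stops and is lost keeps the failing early-termination value or gets 0%. A subject who fails, stops, switches and returns for the Month 12 MRI contributes the post-switch value. Where rescue works, the error favours the drug in the primary test, the responder rate and the secondary tests. The one planned sensitivity analysis does not expose it.

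**Working it through.** **1. The plan's own figure.** Protocol 10.1 sizes the trial with an exact two-sided sign test: n = 9, null rate 0.5, alternative 0.91. Rejecting at 8 or more responders (or 1 or fewer) gives:

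- alpha = 2 × (9 + 1)/512 = 0.0391, printed as 0.04;
- power = 9 × 0.91^8 × 0.09 + 0.91^9 = 0.3809 + 0.4279 = 0.809, printed as 80.9%.

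Both reproduce.

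**2. Which value enters the test.** Each subject contributes one value. Take a subject removed for deterioration who starts another Gaucher drug and is followed to Month 12:

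- The Month 12 MRI exists, so the early-termination scan is not used (SAP 5.3).
- The value is kept because post-discontinuation data are included (SAP 2.1.1, 6.1.1).
- The subject has baseline and Month 12 data and at least one dose, so stays in the per-protocol set (SAP 4).
- The worst-value rule in SAP Appendix 2.1 helps only if both scans fall within 52 weeks ± 42 days. A termination scan at Month 6 does not.

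**3. Effect on one trial (assumed data, n = 9).** Exact Wilcoxon signed-rank test on percent change + 20, as in SAP Appendix 4. T+ is the rank sum of the positive shifted values. Sign patterns with T+ at or below 0, 5, 6, 7, 8 and 13 number 1, 10, 14, 19, 25 and 77 of 512; the two-sided p doubles that share.

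Example A: eight subjects at -24, -27, -31, -34, -38, -42, -46 and -50%, plus one failure.

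| Ninth subject | T+ | p | Responders |
|---|---|---|---|
| fails at 0% | 6 | 28/512 = 0.055 | 8/9 |
| rescued to -35% | 0 | 2/512 = 0.004 | 9/9 |

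Example B: seven subjects at -24, -27, -30, -33, -36, -39 and -42%, plus failures at 0% and -5%.

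| Failures | T+ | p | Responders (95% lower limit) |
|---|---|---|---|
| neither rescued | 13 | 154/512 = 0.30 | 7/9 (40.0%) |
| 0% rescued by another enzyme to -31% | 6 | 28/512 = 0.055 | 8/9 (51.8%) |
| -5% rescued by another enzyme to -28% | 8 | 50/512 = 0.098 | 8/9 (51.8%) |
| both rescued by another enzyme | 0 | 2/512 = 0.004 | 9/9 (66.4%) |
| 0% subject has splenectomy, if scored -100% | 5 | 20/512 = 0.039 | 8/9 (51.8%) |
| -5% subject has splenectomy, if scored -100% | 7 | 38/512 = 0.074 | 8/9 (51.8%) |

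In B, a single enzyme rescue does not turn the primary test, but it does lift the lower limit for the responder rate above the 50% mark in SAP 6.1.2.

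**4. Effect on error rates.** Let f be the share of true non-responders who are rescued and scored as responders at Month 12. The documents give no figure; 0 to 30% is assumed. The scored rate is p = p0 + (1 - p0)f, and the chance of an efficacy finding is 9p^8(1 - p) + p^9.

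| f | True rate 0.5 | True rate 0.91 |
|---|---|---|
| 0 | 0.0195 | 80.9% |
| 10% | 0.0385 | 83.8% |
| 20% | 0.0705 | 86.7% |
| 30% | 0.1211 | 89.4% |

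Simulating the Wilcoxon test itself (200,000 trials, normal percent change with median -20% and SD 10 to 20, rescued values near -35% or at -100%) gives about 0.02, 0.04, 0.06 to 0.08 and 0.11 to 0.13 for the same shares.

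**The case against.** Treatment policy is a declared and legitimate strategy, and the documents contain safeguards: the Gaucher drugs are prohibited during the study, an MRI is due at early termination, baseline is carried forward when no later imaging exists, and follow-up may end 30 days after stopping. The bias needs a chain of failure, stopping, effective rescue, continued follow-up and a Month 12 MRI. The additional treatments in Protocol 6.3.3 need not be Gaucher-specific. Type 3 disease is progressively neurodegenerative and the enzyme has no effect on neurologic involvement (Protocol 4.1, 4.4), so deterioration need not lead to a drug that acts on the spleen.

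These points limit how often the problem can arise. They do not supply the missing rule: the safeguards in SAP 5.3 act only when Month 12 is missing, and Protocol 7.9 does not say what happens to data once a listed drug is taken.

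A reader might go further and infer that the plan deliberately keeps every post-rescue value and scores a splenectomy as -100%. The documents do not support that. Only one value per subject enters the test. Keeping a post-switch value follows from a general rule without an exception, not from a statement about switching. The SAP is silent on an absent spleen: it could be scored as 0 cm³, or treated as missing and replaced under SAP 5.3 by the early-termination MRI, ultrasound or baseline, which could make the subject a failure.

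**Conclusion.** The concern holds as a gap. The SAP does not address three foreseeable events that act directly on the endpoints. As written, a Month 12 MRI on another Gaucher therapy counts toward the efficacy decision, and the per-protocol analysis cannot show its influence. For splenectomy the direction is undetermined until a scoring rule exists.

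The size is conditional. All datasets, rescue effects and rescue shares above are assumptions. If nobody is rescued and followed to Month 12, the primary result is unaffected. With about nine evaluable subjects, one or two such values can decide the primary test; with more of the permitted 15 analysed, each value would weigh less. It would be too strong to say that any single rescue turns a failed trial into a success: Example A does so with one, while Example B needs two enzyme rescues.

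**What to change.** 1. In SAP 2.1.1, 2.1.2, 6.1.1 and 6.2.1, name start of another Gaucher-specific therapy (the Protocol 7.9 list), splenectomy and bone marrow transplant as separate intercurrent events. State that an organ volume after splenectomy is not scored as a reduction.
2. At minimum, prespecify an analysis of the primary, responder and secondary endpoints that uses no value collected after such an event. For spleen and liver, take the last MRI before the event (the early-termination scan), otherwise the SAP 5.3 baseline rule. For hemoglobin, platelets and biomarkers, take the last pre-event value. Count the subject as a non-responder in the responder rate.
3. Preferably base the efficacy conclusion on that analysis and keep the all-data analysis as sensitivity. This is a choice of estimand, and the sponsor should give its reason either way.
4. In SAP 4 and Protocol 10.2, exclude from the per-protocol set anyone who had such an event or stopped study drug before Month 12.
5. Reconcile SAP 6.3, which is labelled treatment policy but excludes data after study drug discontinuation.

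The cost is SAP wording, a matching edit to Protocol 10.2 and one derived flag. Results become less favourable if rescue occurs, and the per-protocol set may shrink when subjects stop early even without rescue.

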2.1.2. Secondary Estimand(s)

There are couple of secondary estimands of this study, which estimate the effect for all participants treated and regardless of whether an intercurrent event occurs. Each of them includes the following 4 attributes:

- Population: All patients who suffer from the Type 3 GD as defined by the inclusion and exclusion criteria, and who have received at least one complete dose (or partial dose if adverse events prevent completing infusion dose);
- Variable:
 - Percent change from baseline to Month 12 in liver volume expressed in MN and measured by MRI;

- Percent change from baseline to Month 12 in hemoglobin;
- Percent change from baseline to Month 12 in platelet;
- Percent change from baseline to Month 12 in Lyso-Gb1 (lyso-glucosylsphingosine);
- Percent change from baseline to Month 12 in chitotriosidase.
- Intercurrent event: All data after an intercurrent event (discontinuation of treatment, discontinuation of study, etc), if collected, will be included;
- Population-level summary: median percent change from baseline to Month 12 and p-value from the Wilcoxon signed ranks test.

2.1.3. Additional Estimand(s)

The responders to the primary efficacy endpoint are defined as participants who had the reduction from baseline greater than 20% in spleen volume MN. The responder rate among all patients received at least one complete dose, will be used as the population-level summary for this alternative estimand.

2.2. Study Design

This is a multicenter study to assess the safety and efficacy of taliglucerase alfa (60 units/kg) in previously untreated subjects of any age with Type 3 GD. Subjects will receive an infusion of taliglucerase alfa every 2 weeks for 12 months. Subjects who tolerate the infusions well for 3 months will be eligible for home therapy based on approval of the Investigator.

Type 3 GD is a very rare genetic orphan disease. This study will not have a placebo control group because it would be unethical to deny patients the possibility to improve their symptomatology with an ERT that has been proved efficacious and safe, not only for Type 1 GD in many countries but also for Type 3 GD in a small number of countries. Thus, all subjects will receive the investigational product in this study.

The parameters chosen as endpoints for this study are the most relevant parameters to GD and allow a significant and relevant evaluation of improvement as a result of treatment for 12 months. Improvement in the clinical manifestations of the disease leads to the achievement of the therapeutic goals of GD treatment in the medical community, which are improved fatigue and decreased risk for morbidities.

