1. SYNOPSIS

TITLE: A Multicenter, Safety and Efficacy Study of Taliglucerase Alfa in Subjects with Type 3 Gaucher Disease
INVESTIGATIONAL PRODUCT: Taliglucerase alfa (plant cell expressed recombinant human glucocerebrosidase)
INDICATION: Gaucher Disease (GD)
PHASE OF DEVELOPMENT: 3B
INVESTIGATIONAL SITES/LOCATIONS: Multicenter, (Israel, India, and Turkey)
INTERNAL PFIZER STUDY NUMBER: WI224302
OBJECTIVES: To assess the safety and efficacy of taliglucerase alfa in untreated subjects (any age) with symptoms and clinical manifestations of Type 3 GD.
STUDY DESIGN: This is a multicenter study to assess the safety and efficacy of taliglucerase alfa (60 units/kg) in previously untreated subjects of any age with Type 3 GD. Subjects will receive an infusion of taliglucerase alfa every 2 weeks for 12 months. Subjects who tolerate the infusions well, and who are treated in centers where home therapy is the SOC will be allowed to switch from site to home treatment at the discretion of the PI but after no less than 3 uneventful infusions at the site.
NUMBER OF SUBJECTS (PLANNED): up to 15
DIAGNOSIS AND MAIN CRITERIA FOR INCLUSION: Key inclusion criteria Eligible subjects must fulfill the following inclusion criteria: 
1. Male or female of any age; however, if female:
• must be using contraception if of childbearing potential or must be surgically sterile• must not be lactating2. Diagnosis of Type 3 GD by enzyme and sequence analysis; and confirmed by the Medical Monitor.3. Splenomegaly at least 5 x multiples of normal (MN).4. Treatment-naïve.

Key exclusion criteria

Eligible subjects may not have any of the following exclusion criteria:

1. Type 2 GD.
2. Presence of myoclonic seizures.
3. At least one allele of:
 - N370S (N409S in recent nomenclature)
 - R496H (R535H in recent nomenclature)
4. Presence of calcification in heart valves or arteries in echocardiography.
5. Presence of untreated iron, folic acid, vitamin B₁₂ deficiency and/or hypothyroidism. (Resolved anemia is not an exclusion criterion.)
6. Presence of human immunodeficiency virus (HIV), hepatitis B surface antigen (HBsAg), and/or hepatitis C infections.
7. Splenectomy and bone marrow transplantation.
8. Presence of any medical, emotional, behavioural, or psychological condition that in the judgment of the Investigator would interfere with the subject's compliance with the requirements of the study.

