6. INVESTIGATIONAL PLAN

6.1 Overall Study Design and Plan – Description

This is a multicenter study to assess the efficacy and safety of taliglucerase alfa (60 units/kg) in previously untreated subjects of any age with Type 3 GD. For the purposes of this study, subjects receiving no Gaucher-specific medications for at least 12 months will be considered “untreated”. Subjects will receive an IV infusion of taliglucerase alfa every 2 weeks for 12 months. Subjects who are treated in centers where home therapy is the SOC will be allowed to switch from site to home treatment at the discretion of the PI but after no less than 3 uneventful infusions at the site. At the end of the 12-month treatment period, eligible subjects will be offered enrollment in an open-label extension study if taliglucerase alfa is not commercially available.

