9. STUDY PROCEDURES AND FLOW CHART

9.1 Study Flow Chart

Table 1: Study Flow Chart

Activity	Visit 0 Screening	Visit 1 Baseline	Visits 2-5	Visit 6	Visit 7 Month 3	Visits 8-13	Visit 14 Month 6	Visits 15-19	Visit 20 Month 9	Visits 21-26	Visit 27 Month 12
	Day -50 ±10	Day 1	Weeks 2, 4, 6, 8, (±3 days)	Week 10 (±3 days)	Week 12 (±7 days)	Weeks 14, 16, 18, 20, 22, 24 (±3 days)	Week 26 (±7 days)	Weeks 28, 30, 32, 34, 36 (±3 days)	Week 38 (±7 days)	Weeks 40, 42, 44, 46, 48, 50 (±3 days)	Week 52 ^d (±7 days)
Sign informed consent	X										
Review inclusion/exclusion criteria	X										
Demographics	X										
Medical history	X										
Current/concomitant medications	X	X	X	X	X	X	X	X	X	X	
Weight/height	X	X			X		X		X		X
Physical examination	X	X			X		X		X		X
Neurologic assessment	X						X				X
Hematology	X	X			X		X		X		X
Biochemistry ^{f,g}	X	X			X		X		X		X
Urinalysis	X	X			X		X		X		X
Serology (HIV, HBsAg, HCV)	X										
TSH, free T4, transferrin, B ₁₂ and folic acid	X										
Beta HCG (post-menarcheal girls)	X										
Vital signs ^h	X	X	X	X	X	X	X	X	X	X	
Anti-taliglucerase alfa antibodies		X				X					X
Organ volumes (MRI)	X										X
Ultrasound (liver and spleen)	X						X				X
Echocardiography	X										
Tanner Stage		X									X
X-ray of left hand and wrist		X									X
DEXA		X									X
mSST	X						X				X
Molecular analysis ^e	X										
Lyso-Gb1 biomarker		X			X		X		X		X
Chitotriosidase		X			X		X		X		X
IV infusion of taliglucerase alfa		X ^a	X ^b	X	X ^c	X	X ^c	X	X ^c	X	X ^c
Observe subject clinically		X	X		X		X		X		X
Evaluate injection site		X	X		X		X		X		X
Adverse events	X	X	X	X	X	X	X	X	X	X	X

DEXA = dual-emission X-ray absorptiometry; HBsAg = hepatitis B surface antigen; HCG = human chorionic gonadotropin; HCV = hepatitis C virus; HIV = human immunodeficiency virus, IV = intravenous; MRI = magnetic resonance imaging; T4 = thyroxine; TSH = thyroid stimulating hormone

- ^a A follow-up telephone call with the subject and/or parent or guardian will be held the day after the infusion.
- ^b Subjects who tolerate the infusions will be eligible for transfer to home or infusion center treatment after this visit at the discretion of the Investigator and Medical Monitor.
- ^c Taliglucerase alfa infusion must be done at the subject's selected medical center.
- ^d All Month 12 (Week 52) procedures/assessments are to be done for any subject who withdraws or is discontinued from the study before completion.

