6. DEXA
7. Taliglucerase alfa infusion
8. Adverse event evaluation

The following procedures will be performed after taliglucerase alfa dosing:

1. Observe the subject clinically for a minimum of 1 hour post-dosing.
2. Evaluate vital signs pre and post infusion, and as needed if an AE occurs during infusion. Evaluate the injection site.
3. A follow up telephone call with the subject and/or parent or guardian will be held the day after the infusion.

The subject and/or parent or guardian will be reminded of the date of the next visit.

9.2.3 Visits 2 – 5 (Weeks 2, 4, 6, and 8 ± 3 Days)

Subjects will receive their taliglucerase alfa infusion at their selected medical center. The following procedures will be performed post-dosing:

1. Observe the subject clinically for a minimum of 1 hour post-dosing.
2. Evaluate vital signs pre and post infusion, and as needed if an AE occurs during infusion.
3. Evaluate the injection site.

Adverse events and concomitant medications will be recorded at each visit.

Subjects will only receive transfusions at the medical center where they will be followed up and treated. The procedures to be followed will depend on local standards of care and procedures established at the medical center. Minimally, safety data (vital signs, adverse events, concomitant medications) will be recorded at each bi-weekly treatment with taliglucerase alfa administered at the medical center.

The subject and/or parent or guardian will be reminded of the date of the next visit.

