9.2.4 Visit 6 (Week 10 ± 3 Days)

Subjects will receive their taliglucerase alfa infusion at their selected medical center. The following procedures will be performed post-dosing:

1. Adverse event evaluation.
2. Concomitant medications.
3. Vital signs pre and post infusion, and as needed if an AE occurs during infusion.

The subject and/or parent or guardian will be reminded of the date of the next infusion/visit.

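### The protocol contradicts itself on whether, when and on whose approval infusions may move off site, and the SAP adds a further version

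*SAP*

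**What the plan says.** Four current statements bear on where infusions are given.

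- **Protocol synopsis and section 6.1.** Section 6.1 reads "Subjects who are treated in centers where home therapy is the SOC will be allowed to switch from site to home treatment". The decision is "at the discretion of the PI but after no less than 3 uneventful infusions at the site" (synopsis; section 6.1 carries the same minimum). The synopsis also asks for good tolerance of the infusions, which section 6.1 leaves out.
- **Protocol Table 1, footnote b**, attached to the infusion cell for Visits 2–5. Subjects who tolerate the infusions are "eligible for transfer to home or infusion center treatment after this visit at the discretion of the Investigator and Medical Monitor".
- **Protocol sections 9.2.3 to 9.2.10.** The visit descriptions put the infusion at the center. Section 9.2.4, for example, says "Subjects will receive their taliglucerase alfa infusion at their selected medical center", and the sections for Visits 8–13, 15–19 and 21–26 say the same. Section 9.2.3 adds "Subjects will only receive transfusions at the medical center where they will be followed up and treated". It writes *transfusions*, but the context is the study infusion.
- **SAP section 2.2.** "Subjects who tolerate the infusions well for 3 months will be eligible for home therapy", on the Investigator's approval.

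Footnote c of Table 1 fixes the infusions at Visits 7, 14, 20 and 27 at the subject's medical center.

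**The concern.** The statements disagree on four things: whether off-site infusion is allowed at all, how soon, who approves it, and whether it depends on local standard of care. Three of the four are in the protocol, which is the document sites work from. A site that sends a subject home under section 6.1 departs from section 9.2. A site that follows section 9.2 makes no use of an option that section 6.1 and footnote b both grant.

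The study is multicenter with at most 15 subjects, and safety is a stated objective. Sites could follow different rules in good faith, and the length of on-site supervision would then vary by site. The drug has a known reaction profile. Section 5.1 of the appended label reports hypersensitivity in 21 of 72 patients (29%) and signs consistent with anaphylaxis in 2 of 72 (3%), with reactions up to 3 hours after the start of infusion.

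**Working it through.** There is no plan figure to reproduce. The check maps each rule onto the protocol's own visit schedule.

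**Inputs**
- Visits 1 to 27 each carry an infusion, so there are 27 infusions. Visit v falls at Week 2(v − 1) (Table 1).
- Visits 7, 14, 20 and 27 must be at the center (footnote c).
- Month 3 is Visit 7, Week 12 (section 9.2.5).

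**Formula.** If f is the first visit that may be off site, the off-site maximum is (27 − f + 1) minus the fixed visits from f onward.

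| Text | Site infusions before the move | First off-site visit | Off-site maximum |
|---|---|---|---|
| Synopsis and 6.1 (standard-of-care centers only) | 3 | Visit 4, Week 6 | 24 − 4 = 20 |
| Footnote b, if the visit meant is Visit 2 | 2 | Visit 3, Week 4 | 25 − 4 = 21 |
| Footnote b, if the visit meant is Visit 5 | 5 | Visit 6, Week 10 | 22 − 4 = 18 |
| SAP 2.2 | 7 | Visit 8, Week 14 | 20 − 3 = 17 |
| Sections 9.2.3–9.2.10 | all | none | 0 |

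Footnote b covers a cell of four visits and does not say which one it means, so it gives a range of 18 to 21. Read at Visit 2, it allows the move after two infusions, below the minimum in section 6.1 ("but after no less than 3 uneventful infusions at the site"). At a center where home therapy is not standard of care, the section 6.1 figure is 0, while footnote b and the SAP carry no such limit.

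**Approver.** Synopsis and 6.1: the principal investigator. Footnote b: the Investigator and the Medical Monitor. SAP 2.2: the Investigator. Section 9.2: none, since no move is described.

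**What is scheduled wherever the infusion is given**
- Table 1 marks adverse events at every visit. It marks vital signs through Visits 21–26, and footnote h carries pre- and post-infusion vital signs to Visit 27.
- SAP 3.5.3 collects vital signs at each infusion.
- The Appendix 3 hypersensitivity algorithm is not limited to infusions at the site.
- Section 2.2 of the appended label calls for a healthcare professional's supervision.

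**What depends on location**
- Clinical observation and the injection-site check are scheduled at Visits 1–5, 7, 14, 20 and 27. Visits 6, 8–13, 15–19 and 21–26 list neither, even at the center. A move could therefore displace these two items only at Visits 3–5 (footnote b at its earliest) or Visits 4–5 (section 6.1).
- The minimum safety data in section 9.2.3 are stated for treatment given at the medical center. No part of section 9.2 describes procedures for an infusion elsewhere.

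**The case against.** A reader might infer that safety supervision is undefined. The documents do not support that: adverse events and vital signs are scheduled without reference to location, and Appendix 3 covers any infusion. A reader might also infer that most safety data would be lost at home. That fails too, because most infusion visits list only adverse events, concomitant medications and vital signs, even at the center.

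Other objections have some force.

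- **The first two rules can be reconciled on timing.** Three site infusions are complete at Visit 3, inside the cell that carries footnote b. This is fair, but the approver and the standard-of-care condition still differ.
- **The SAP sentence is only a design summary.** Sites do not infuse under the SAP, so it is the least important of the four texts. The conflict inside the protocol remains without it.
- **Section 9.2.3 says transfusions.** Read literally, its restriction would not cover the study drug. The other sentences of section 9.2 still place each infusion at the center.
- **Section 9.2 may simply mean that there is no home therapy.** Footnote c would then be redundant, since it fixes four visits at the center as if others could be elsewhere. Sections 9.2.7, 9.2.9 and 9.2.11 also speak of subjects returning to the center.
- **The 29% is a per-patient rate from earlier trials.** It does not measure the risk of home infusion or of a reaction after several uneventful infusions. It shows only that the rule is relevant to safety.

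**Conclusion.** The inconsistency is real, is in current text, and lies mainly within the protocol. The earliest off-site infusion ranges from Week 4 to never, and the number that may be given off site from 0 to 21 of 27. The timing, the approver and the standard-of-care condition all conflict, and section 9.2 gives no procedures for an off-site infusion.

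The counts are maxima. They assume that all 27 infusions are given, that the early ones are uneventful, that approval comes at the first opportunity, and that the selected medical center in section 9.2 means the study site.

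The statistical consequence is limited. The organ-volume, laboratory and biomarker assessments behind the primary and secondary endpoints fall at screening, baseline and the visits fixed at the center. No analysis set depends on where infusions are given. Power, alpha and the primary analysis are untouched. The point should be corrected because sites cannot follow all of the protocol as written on a safety-relevant matter. Which rule is right is a clinical decision on which this review takes no position.

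**What to change.** The sponsor's clinical team should reconcile the synopsis, section 6.1, Table 1 footnote b and sections 9.2.3 to 9.2.10 into one rule. It should state:

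- whether off-site infusion is allowed;
- if so, from which visit or after how many infusions;
- one named approver or set of approvers;
- one position on the standard-of-care condition;
- whether infusion centers are covered as well as homes.

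Correct the word *transfusions* in section 9.2.3 if infusions are meant, and align SAP 2.2 with the result. If off-site infusion is kept, section 9.2 should say that the safety data listed for each infusion visit are also recorded for off-site infusions, and by whom.

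The cost is wording in a protocol amendment and a matching SAP edit. No assessment, sample size or analysis needs to change.
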